Mitigating Automation Bias in Physician-LLM Diagnostic Reasoning Using Behavioral Nudges

[name], [name], [name],
[name], [name]

Study Protocol and Statistical Analysis Plan

Document Date: December 26, 2025

1 Introduction

Automation bias presents substantial risks in clinical environments, particularly as artificial intelligence (AI) tools become more integrated into healthcare workflows. This cognitive phenomenon describes the tendency of individuals to favor suggestions from automated decision-making systems, even when those suggestions are incorrect. While Large Language Models (LLMs), such as ChatGPT-5.1, hold promise for reducing diagnostic errors by augmenting clinical reasoning, concerns arise about their potential to amplify cognitive biases. Of particular concern is the propensity of LLMs to *hallucinate*, generating plausible but false information, which, when combined with automation bias, can lead clinicians to accept erroneous recommendations without adequate scrutiny.

The emergence of automation bias in medical contexts reflects a complex interplay of environmental and psychological factors. Time constraints in high-volume clinical settings create pressure to accept AI-generated recommendations without adequate scrutiny. Financial incentives that prioritize efficiency over thoroughness may further discourage the critical evaluation necessary for sound clinical judgment. Cognitive fatigue during extended shifts diminishes physicians' capacity for sustained analytical thinking. These contextual pressures interact with psychological mechanisms including diffusion of responsibility, overconfidence in technological solutions, and cognitive offloading, collectively creating conditions where uncritical acceptance of AI-generated recommendations becomes more likely.

This randomized controlled trial evaluates the effectiveness of a behavioral nudge intervention designed to mitigate automation bias among medical doctors utilizing LLM-generated diagnostic recommendations. The primary objective is to determine whether this intervention improves diagnostic reasoning performance scores when physicians evaluate clinical vignettes that include deliberately flawed LLM recommendations. Secondary objectives include assessing whether physician experience level, gender, and prior LLM experience moderate the intervention's effectiveness.

Participants will be randomly assigned to control or treatment arms. Both groups will evaluate six clinical vignettes accompanied by LLM-generated recommendations, three of which contain deliberately introduced errors that are subtle yet clinically significant. LLM consultation will be discretionary, physicians will choose whether to view ChatGPT recommendations for each case.

The control arm will receive these recommendations without additional context. The treatment arm will receive a behavioral nudge intervention leveraging complementary cognitive mechanisms: (1) an anchoring cue displaying ChatGPT's average diagnostic reasoning accuracy on standard medical datasets before evaluation begins, establishing realistic performance expectations, and (2) a selective attention cue enabling deeper System 2 engagement through color-coded confidence signals when participants view ChatGPT recommendations. These confidence signals are generated through ensemble assessment: three independent state-of-the-art LLMs (Claude Sonnet 4.5, Gemini 2.5 Pro Thinking, and GPT-5.1) each provide confidence ratings for the recommendation, and the mean confidence determines the signal color. Multi-model aggregation mitigates the systematic overconfidence of single-model confidence reports, yielding more robust uncertainty estimates. Red signals indicate mean confidence below ChatGPT's baseline accuracy on medical benchmarks, prompting heightened critical scrutiny. Orange signals indicate above-baseline but less than 100% confidence, deliberately using orange rather than yellow to prevent complacency. Green signals indicate high ensemble confidence ($= 100\%$), though standard AI safety warnings apply (e.g., "AI may make mistakes. Always double-check.").

Clinical vignettes will be randomly sequenced to prevent pattern detection. By comparing diagnostic accuracy scores between arms, we will quantify the degree of automation bias in the control group and assess whether the behavioral nudge intervention reduces uncritical acceptance of erroneous AI-generated recommendations in the treatment group. This design enables

us to isolate both the magnitude of automation bias and the causal impact of transparency-based interventions on physician decision-making.

All participants will complete a comprehensive AI-literacy training program covering LLM capabilities, limitations, prompt engineering techniques, and output evaluation strategies before beginning the trial. Responses will be evaluated by blinded reviewers using an expert-developed assessment rubric specifically designed to detect uncritical acceptance of erroneous information. This naturalistic approach will yield insights directly applicable to real clinical workflows, where increasing cognitive demands can progressively impact diagnostic decision quality, while providing evidence on scalable interventions to preserve clinical judgment in AI-augmented diagnostic settings.

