1.2 Hypotheses

- **Primary Hypothesis (H1):** Physicians receiving the behavioral nudge intervention (baseline accuracy information and case-specific color-coded confidence signals) will demonstrate significantly higher diagnostic reasoning scores when evaluating clinical vignettes with deliberately flawed LLM recommendations compared to physicians receiving the same LLM recommendations without the nudge.
- **Secondary Hypotheses:**
 - **H2:** Physicians with less clinical experience will exhibit greater baseline automation bias and show larger treatment effects from the nudge intervention compared to more experienced clinicians.
 - **H3:** The intervention will demonstrate greater effectiveness for red-signal (below-baseline) versus orange-signal (above-baseline) recommendations.

2 Methods

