 - **Orange Signal:** Displayed when the ensemble confidence exceeds the established baseline average but remains below 100%. The choice of orange (vs. yellow) is a deliberate nudge to prevent automation bias and maintain clinical scrutiny.
 - **Green Signal:** Displayed when the ensemble reaches a consensus of 100% confidence. Standard caution will apply (e.g., “AI may make mistakes. Always double-check.”) to guard against over-reliance.

Randomization: Participants will be randomly assigned to either the intervention or control arm in a 1:1 ratio using a computer-generated random number sequence.

Blinding: Outcome assessors (those scoring the diagnostic reasoning performance) will be blinded to the participants’ group assignments. Participants will be blinded to the study’s specific hypothesis regarding automation bias but will be informed they are evaluating LLM diagnostic assistance tools.

Measuring change in automation bias: The primary measure of the change in automation bias will be the mean difference in diagnostic reasoning accuracy scores between the treatment and control arms. A positive difference favoring the treatment arm will indicate the reduction in automation bias attributable to the nudge.

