3.1 Primary Outcome

Diagnostic Reasoning Accuracy Score: This will be a composite score (expressed as a percentage) based on a structured rubric that evaluates the following components for each clinical vignette:

1. **Quality of Differential Diagnoses:** (0-3 points)
 - 0: No reasonable differential diagnoses listed.
 - 1: One reasonable differential diagnosis listed.
 - 2: Two reasonable differential diagnoses listed.
 - 3: Three or more reasonable differential diagnoses listed, including the correct diagnosis.
2. **Supporting Findings:** (0-1 points per diagnosis)
 - 0: No relevant supporting findings listed.
 - 1: Some relevant supporting findings listed, but incomplete.
 - 2: Comprehensive list of relevant supporting findings.
3. **Opposing Findings:** (0-1 points per diagnosis)
 - 0: No relevant opposing findings listed.
 - 1: Some relevant opposing findings listed, but incomplete.
 - 2: Comprehensive list of relevant opposing findings.
4. **Top Choice Diagnosis Accuracy:** (0-18 points)
 - 0: Incorrect final diagnosis.
 - 9: Partially correct final diagnosis (e.g., correct category but wrong specific diagnosis).
 - 18: Correct final diagnosis.
5. **Appropriateness of Next Steps:** (0-1 points per step)
 - 0: Inappropriate or unnecessary next steps.
 - 0.5: Partially appropriate next steps (e.g., some necessary tests missing).
 - 1: Appropriate and comprehensive next steps.

The total score for each vignette will be the sum of these components.

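### The comparison between arms estimates the nudge's effect, not the level of automation bias in controls, and the first half of H2 has no defined measure

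*Combined protocol and SAP*

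**What the plan says.** The Introduction makes two claims about a level. It says of the score comparison between arms that "we will quantify the degree of automation bias in the control group", and that the design makes it possible to "isolate both the magnitude of automation bias and the causal impact of transparency-based interventions on physician decision-making". It also describes the scoring rubric as "specifically designed to detect uncritical acceptance of erroneous information".

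Section 1.2 builds on the idea of a level. The first half of H2 reads "Physicians with less clinical experience will exhibit greater baseline automation bias"; the second half predicts larger treatment effects in the same physicians.

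Section 2.1 is narrower. It defines a measure only for the change in automation bias, namely the mean score difference between arms: "A positive difference favoring the treatment arm will indicate the reduction in automation bias attributable to the nudge".

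The rubric in section 3.1 awards points for differentials, supporting and opposing findings, final diagnosis and next steps. The heaviest item runs from "0: Incorrect final diagnosis" through 9 points for a partly correct answer to 18 for a correct one.

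**The concern.** A difference between two arms that both have access to the advice describes what the nudge changes. It does not say how much automation bias the controls had. If the difference were zero, the controls could have had none or a great deal.

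Two things are at stake. The plan claims a property that its design lacks, and that claim could pass into the report. Also, half of a stated secondary hypothesis has no variable, so any level of bias reported later would rest on a measure chosen after the data were seen. Without a record of whether the planted error was repeated, a higher score is only indirect evidence of less uncritical acceptance.

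**Working it through.** **1. The plan's own figure.** Section 2.3 gives 25 per arm, a difference of 8 points, SD 16.2, ICC 0.05 to 0.15, 4 cases per participant and two-sided alpha 0.05. Reading 16.2 as the case-level SD, the SD of a participant mean is 16.2 × sqrt((1 + 3 × ICC)/4).

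| ICC | SD of participant mean | Power, normal | Power, t with 48 df |
|---|---|---|---|
| 0.05 | 8.686 | 90.3% | 89.1% |
| 0.10 | 9.235 | 86.5% | 85.1% |
| 0.15 | 9.754 | 82.6% | 81.1% |

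The stated power of at least 80% reproduces on that reading. It is power for the arm difference only. The problem below is one of identification, which sample size does not affect.

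**2. What the arm difference identifies.** On flawed vignettes, let U be the score without LLM advice, B the points that controls lose to automation bias, and r the nudge effect. Then control = U − B, treatment = U − B + r, and the difference = r. Both U and B drop out. With r = 8 (section 2.3) and illustrative values of U and B that are not in the documents:

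| U | B | Control | Treatment | Difference |
|---|---|---|---|---|
| 60 | 8 | 52 | 60 | 8 |
| 70 | 18 | 52 | 60 | 8 |
| 80 | 28 | 52 | 60 | 8 |

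The observed data are identical in all three rows. To recover B one needs U, and nothing planned supplies it. Section 2.1 gives both arms the recommendations, and section 2.5.1 collects no answer before the panel is opened. Section 5.1 speaks of controls working without LLM help, but this conflicts with the Introduction and section 2.1 and cannot stand in for an unaided arm.

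**3. Flawed against accurate vignettes within controls.** Section 2.4 fixes one recommendation per vignette for all participants. The control-arm gap is therefore the effect of the flaw plus the difference in mean difficulty between two different sets of three cases. More participants do not separate the two. The model in section 4.2 has no flawed/accurate term, and its random vignette effect cannot separate them either. The nearest planned comparison, scores by signal colour and group in section 4.6, is exploratory, is not presented as a measure of bias and is not split by experience.

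**4. The rubric.** No item in section 3.1 asks whether an answer repeats the planted error. On the final-diagnosis item, a repeated error scores 0, or 9 if its category is right; an unrelated wrong diagnosis can earn the same points. The score does not show where an error came from.

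**5. H2.** Section 4.4 examines whether the intervention's effect varies with experience, which serves the second half. Years of practice in section 4.2 is a covariate for overall score. No analysis relates experience to a defined measure of automation bias.

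**6. Data already available.** Section 2.5.1 records differentials, findings for and against, final diagnosis, next steps and whether the panel was viewed. Three flawed vignettes give 50 × 3 = 150 responses in all and 25 × 3 = 75 among controls.

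**The case against.** The strongest reply is that the operative text is already right. Section 2.1 defines a change, and the primary objective, H1 and the analysis in section 4.2 need no control-arm level. This stands: the randomised comparison of scores is not in question. But the level is claimed twice in the Introduction and H2 depends on it, so more than one loose sentence is affected.

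Several stronger readings are tempting, and the documents do not support them:

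- **That the first half of H2 is unanswerable.** It is undefined, not unanswerable. It compares less with more experienced physicians on the same vignettes, so common difficulty cancels. Only difficulty that varies with experience would remain.
- **That difficulty noise swamps the 8-point nudge effect.** Both arms see the same vignettes, so common difficulty cancels there too, and a flawed-minus-accurate gap is not comparable with it. The documents give no between-vignette SD.
- **That a copied error and an unrelated wrong diagnosis always score the same.** This can be so on the final-diagnosis item, but not when the copied error earns 9, and it need not be so for the composite. Section 2.4 plants reasoning errors, which may not appear in the final diagnosis at all.
- **That fewer panel openings would be a rival explanation.** The Introduction defines automation bias as favouring automated suggestions, so opening the panel less may be part of the effect. It should be reported, not treated as a flaw.
- **That an error-adoption rate in controls would be the missing level.** Some physicians would make the same error unaided or without opening the panel, so the rate mixes spontaneous error with automation bias.
- **That error status should be randomised within vignette.** This conflicts with the feature in section 2.4 that everyone sees the same recommendation for a vignette. It would also contrast flawed with accurate advice, not advice with none.

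**Conclusion.** The concern holds in a limited form. The arm comparison identifies the change attributable to the nudge and leaves the control-arm level undetermined at any sample size. This rests on the design as written: both arms have access, there is no unaided answer, and error status is fixed by vignette. The values of 8, 18 and 28 points only illustrate the argument.

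The rubric does not measure acceptance of the planted error in the way the Introduction says, and the first half of H2 lacks a variable and an analysis. The second half of H2 has its planned subgroup analysis. The matter should be corrected before scoring.

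**What to change.** 1. **Wording.** In the Introduction, state that the arm comparison estimates the change attributable to the nudge. Delete the claims to quantify or isolate the level of automation bias.
2. **One added code.** Before scoring starts, define for each flawed vignette what counts as repeating the planted error in any recorded field: differentials, supporting or opposing findings, final diagnosis or next steps. The existing blinded raters code it yes or no.
3. **Analysis by arm.** Compare the error-adoption rate in all randomised participants with a logistic mixed model. Beside it, report panel-opening rates by arm and adoption by viewed or not viewed. Keep these descriptive, because viewing is the participant's choice.
4. **H2, first half.** Use adoption by experience within controls, labelled exploratory. About 25 physicians and 75 responses on three vignettes will give limited precision.
5. **Label.** Call the measure agreement with the planted error, not the causal level of automation bias.

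The cost is some rewording, three short definitions and one code on at most 150 responses. The primary outcome, sample size and vignettes do not change.

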1.1 Research Question

Does a behavioral nudge intervention combining baseline ChatGPT accuracy information and case-specific color-coded confidence signals reduce automation bias and improve diagnostic reasoning accuracy among physicians with discretionary access to LLM recommendations?

1.2 Hypotheses

- **Primary Hypothesis (H1):** Physicians receiving the behavioral nudge intervention (baseline accuracy information and case-specific color-coded confidence signals) will demonstrate significantly higher diagnostic reasoning scores when evaluating clinical vignettes with deliberately flawed LLM recommendations compared to physicians receiving the same LLM recommendations without the nudge.
- **Secondary Hypotheses:**
 - **H2:** Physicians with less clinical experience will exhibit greater baseline automation bias and show larger treatment effects from the nudge intervention compared to more experienced clinicians.
 - **H3:** The intervention will demonstrate greater effectiveness for red-signal (below-baseline) versus orange-signal (above-baseline) recommendations.

2 Methods

2.1 Study Design

This study will be a single-blind, randomized controlled trial with two parallel arms. Participants will be randomly assigned in a 1:1 ratio to the intervention arm or to the control arm. To control for variability in user prompting skills, participants will not interact directly with a live LLM chat interface. Instead, they will use a custom-built web platform that displays the clinical vignette and provides access to pre-generated LLM recommendations.

- **Control Arm:** Participants will evaluate six clinical vignettes (three with deliberately flawed diagnostic information and three with correct information). Through the study platform, they will be able to view “LLM Diagnostic Recommendations” generated by ChatGPT. These recommendations will be presented in a standard, neutral text format without additional context or nudge.
- **Intervention Arm:** Participants will evaluate the same six clinical vignettes using the same web platform, but with a behavioral nudge embedded directly within the LLM suggestion interface. Upon expanding the LLM recommendation panel for any vignette, participants will be presented with two synchronized cognitive cues:

1. **Anchoring Cue:** Displayed at the top of the panel, this visual cue presents ChatGPT’s baseline diagnostic accuracy on standard medical datasets (e.g., Medbullets). This serves to explicitly anchor expectations to the model’s realistic performance level, preventing both excessive skepticism and uncritical acceptance, before the participant reads the specific recommendation.
2. **Selective Attention Cue:** Below the baseline accuracy information, each case-specific LLM recommendation will be displayed alongside a color-coded signal reflecting the ensemble confidence for that particular recommendation. This score is derived from a consensus evaluation by three independent state-of-the-art LLMs (e.g., Claude 4.5 Sonnet, Gemini 2.5 Pro Thinking, and GPT-5.1) to mitigate single-model miscalibration:
 - **Red Signal:** Displayed when the ensemble’s mean confidence falls below ChatGPT’s established baseline accuracy, signaling a high-uncertainty case that requires deeper critical evaluation and indicating “*The LLM is less sure about this case than it usually is*”.
 - **Orange Signal:** Displayed when the ensemble confidence exceeds the established baseline average but remains below 100%. The choice of orange (vs. yellow) is a deliberate nudge to prevent automation bias and maintain clinical scrutiny.
 - **Green Signal:** Displayed when the ensemble reaches a consensus of 100% confidence. Standard caution will apply (e.g., “AI may make mistakes. Always double-check.”) to guard against over-reliance.

Randomization: Participants will be randomly assigned to either the intervention or control arm in a 1:1 ratio using a computer-generated random number sequence.

Blinding: Outcome assessors (those scoring the diagnostic reasoning performance) will be blinded to the participants’ group assignments. Participants will be blinded to the study’s specific hypothesis regarding automation bias but will be informed they are evaluating LLM diagnostic assistance tools.

Measuring change in automation bias: The primary measure of the change in automation bias will be the mean difference in diagnostic reasoning accuracy scores between the treatment and control arms. A positive difference favoring the treatment arm will indicate the reduction in automation bias attributable to the nudge.

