4.1 Descriptive Statistics

- Baseline characteristics will be summarized using means and standard deviations for continuous variables (e.g., years of experience) and frequencies and percentages for categorical variables (e.g., gender, specialty).
- Diagnostic reasoning scores and top choice diagnosis accuracy will be summarized using descriptive statistics by group
- LLM consultation rate: For each vignette, a binary indicator will be recorded (1 = participant viewed LLM recommendations; 0 = did not view). The measure is the mean proportion of vignettes (range 0-1) per participant in which recommendations were accessed.

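### Section 2.1 labels any positive score difference as reduced automation bias, although part of it could come from physicians opening the LLM panel less often, and no planned analysis would show this

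*Combined protocol and SAP*

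**What the plan says.** Section 1 makes use of the tool optional in both arms: "LLM consultation will be discretionary, physicians will choose whether to view ChatGPT recommendations for each case". It gives the aim as to "assess whether the behavioral nudge intervention reduces uncritical acceptance of erroneous AI-generated recommendations in the treatment group".

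Section 2.1 places the nudge inside the optional panel: "Upon expanding the LLM recommendation panel for any vignette, participants will be presented with two synchronized cognitive cues". Section 1 instead shows the accuracy figure "before evaluation begins, establishing realistic performance expectations". Section 2.1 describes the purpose of that anchoring cue as "preventing both excessive skepticism and uncritical acceptance".

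The interpretation rule in Section 2.1 carries no condition: "A positive difference favoring the treatment arm will indicate the reduction in automation bias attributable to the nudge". H1 in Section 1.2 concerns performance "when evaluating clinical vignettes with deliberately flawed LLM recommendations", but the model in Section 4.2 neither restricts to flawed vignettes nor has a term for vignette type. As written it covers all six.

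Section 2.5.1 records viewing as 0 or 1 for every vignette. Section 4.1 is the only place that uses it: "The measure is the mean proportion of vignettes (range 0-1) per participant in which recommendations were accessed". That summary pools flawed and accurate cases. The bullet above it, on scores, specifies a summary by group; the consultation bullet does not. Sections 4.2 to 4.6 do not mention the indicator.

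**The concern.** All six vignettes are completed in one session (Section 2.4). A treated physician who sees the accuracy figure and a warning colour early on may open the panel less often afterwards. If the accuracy figure is shown before evaluation starts, as Section 1 says, opening could be affected from the first case.

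Someone who does not open a flawed recommendation has neither accepted it nor scrutinised it. If flawed recommendations lower the scores of those who read them, as the trial presumes, the score on that case improves all the same. Section 2.1 would then report reduced automation bias.

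Better scrutiny of what is read and less reading of the tool are different findings, with different implications for deploying the nudge. On accurate cases, less reading also gives up whatever help the tool provides. Disuse could therefore create an apparent benefit or hide a real one, and the planned analyses would not show which.

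**Working it through.** **The plan's own figure.** Inputs from Section 2.3: 25 per arm, difference 8 points, SD 16.2 (taken as the per-case SD), m = 4 cases, ICC 0.05 to 0.15. The SD of a participant mean is 16.2 × √[(1 + (m − 1) × ICC)/m]. At ICC 0.15 this is 16.2 × √(1.45/4) = 9.75, and the standard error of the arm difference is 9.75 × √(2/25) = 2.76. Power is 82.6% by the normal formula and 81.1% by t. At ICC 0.05 the figures are 90.3% and 89.1%. The stated 80% is reproduced and is not in dispute.

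**Two sources of a gain on flawed cases.** Let v₀ and v₁ be the opening rates in the control and treated arms, d = v₀ − v₁, and L₀ and L₁ the average points lost by reading a flawed recommendation in each arm. If unopened cases score the same in both arms, the flawed-case difference is

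v₀L₀ − v₁L₁ = d × L₀ + v₁ × (L₀ − L₁).

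The first term is disuse and the second is better scrutiny. The score difference gives only their sum.

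**Disuse alone (L₀ = L₁ = L).** Let b be the points gained by reading an accurate recommendation. Physicians cannot know which type a case is before opening it, so I take the same d for both types.

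- Three flawed vignettes: + d × L
- Three accurate vignettes: − d × b
- All six: d × (L − b)/2

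The documents give no value for d, L or b. All three are assumptions:

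| d | L | b | Flawed | Accurate | All six |
|---|---|---|---|---|---|
| 0.2 | 20 | 0 | +4 | 0 | +2 |
| 0.2 | 20 | 20 | +4 | −4 | 0 |
| 0.2 | 40 | 0 | +8 | 0 | +4 |
| 0.2 | 40 | 20 | +8 | −4 | +2 |
| 0.2 | 40 | 40 | +8 | −8 | 0 |
| 0.4 | 20 | 0 | +8 | 0 | +4 |
| 0.4 | 20 | 30 | +8 | −12 | −2 |
| 0.4 | 30 | 0 | +12 | 0 | +6 |

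If disuse can begin only after a first opening, at most 5 of 6 cases are affected and each figure is multiplied by 5/6. The first row then gives +3.3 on flawed cases and +1.7 over six.

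**Is L = 20 or 40 plausible?** The final diagnosis carries 18 points (Section 3.1). Assuming three diagnoses and three next steps, a case totals 3 + 3 + 3 + 18 + 3 = 30 points, or 3 + 6 + 6 + 18 + 3 = 36 if findings score up to 2 each (the section shows both scales). A wrong final diagnosis alone then costs 50% to 60% of the case score. L = 20 requires reading to turn a right final diagnosis wrong in about 33% to 40% of flawed cases. L = 40 requires about 67% to 80%, which is demanding.

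**Against the significance threshold.** At ICC 0.15 the smallest significant six-vignette difference is 1.96 × 16.2 × √(1.75/6) × √(2/25) = 4.9 points. None of the d = 0.2 rows reaches it by disuse alone. The d = 0.4, L = 30, b = 0 row does. For flawed cases only (m = 3) the threshold is 5.9 points.

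**The case against.** The strongest reply is that Section 1.1 asks about physicians with discretionary access. A change in consultation is then part of the intervention's effect, and the randomised contrast captures it correctly. That stands: the comparison is valid as the total effect of assignment, and a reader who inferred that it is confounded or invalid would be wrong. The reply does not rescue the label, because Section 1 defines the target as less uncritical acceptance.

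A reader might also infer that disuse would deliver the whole assumed 8-point effect. The documents do not support that. Both the rule in Section 2.1 and the model in Section 4.2 cover six vignettes, so a flawed-case gain is at least halved and is then offset by lost help on accurate cases. With b = 0, reaching +8 over six vignettes needs d = 0.8 for L = 20, or 0.4 for L = 40.

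Nor do the documents show that opening will fall. The red message is specific to its case, and orange or green signals might sustain use. Under the wording of Section 2.1, a physician who never opens the panel receives no nudge. The mechanism is possible, not established.

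It is also tempting to call disuse a failure on the plan's own terms. The phrase about excessive skepticism describes the anchoring cue only, so it supports the concern without settling it.

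Finally, Section 4.6 compares scores by signal colour and group, which could reveal gains on red-signal cases with losses elsewhere. That is partial help. The analysis is exploratory and takes no account of whether the panel was opened.

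**Conclusion.** The point holds as a fault of interpretation and of missing analysis. Any gain from leaving flawed recommendations unopened would be reported as less uncritical acceptance, and nothing planned would separate the two.

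The disuse component is d × L on the flawed cases named in H1 and d × (L − b)/2 on the primary six-vignette comparison. At d = 0.2 the latter is at most +2 points for L = 20 and +4 for L = 40. It is zero when b equals L and negative beyond that. These sizes rest on assumed d, L and b, on the same d for both case types, and on unopened cases scoring alike in the two arms. The mismatch between H1 and Section 4.2 over which cases count is a separate matter, but it determines which expression applies.

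**What to change.** 1. **Reword the rule in Section 2.1.** For example: *the arm difference is the total effect of offering the nudge, including any change in LLM consultation; by itself it is not evidence of reduced uncritical acceptance*.
2. **Add to Section 4.3 an analysis of the viewing indicator by arm.** Use a logistic mixed model with participant and vignette random effects and an arm × flawed/accurate term. Report the arm difference with its 95% interval and set no pass/fail gate. With 25 per arm, six vignettes, assumed viewing of 50% to 80% and an assumed within-participant ICC of 0.3, the half-width is 1.96 × √[2 × p(1 − p) × (2.5/6)/25], or 14 to 18 percentage points. A gate could not reliably exclude a drop near 0.2. Vignette position may be explored for carry-over.
3. **Report the score difference separately for flawed and accurate vignettes**, through an arm × vignette-accuracy term, so that gains on one and losses on the other are both visible.
4. **Label any comparison among viewed cases as non-randomised**, because viewing happens after randomisation.
5. **Reconcile Sections 1 and 2.1** on when the accuracy cue is shown, since this decides whether opening can be affected from the first case.

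The cost is one or two extra models on data already collected and a narrower reading of a positive result. The estimates by case type and the viewing comparison will be imprecise at this sample size and should be presented that way.
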